
Date: May 10, 2016

Principal Investigator: [name].

Application Number: NA_00041441

2. Objectives (include all primary and secondary objectives)

Primary Objective: To determine which FES ergometry dosing regimen results in the most significant increase in CSF BDNF levels in subjects with inflammatory myelopathy. We will test the hypothesis that 5 FES cycling sessions per week result in greater increase in CSF BDNF concentrations as compared to 1 or 3 sessions and passive cycling.

- a. We will measure CSF concentrations of BDNF in response to FES ergometry (**primary outcome**).
- b. We will investigate whether there is a correlation between plasma and CSF BDNF concentrations.

Secondary Objective: To quantify changes in the CNS inflammatory environment in response to FES ergometry in subjects with inflammatory myelopathy. We will test the hypothesis that concentrations of IL-6, IL17, TNF α , IL-1 β , IL-23, and IL-12 change in response to FES ergometry.

- a. We will measure CSF concentrations of IL-6, IL17, TNF α , IL-1 β , IL-23, and IL-12 in response to FES ergometry.

3. Background (briefly describe pre-clinical and clinical data, current experience with procedures, drug or device, and any other relevant information to justify the research)

Multiple sclerosis (MS) is an inflammatory demyelinating disease of the central nervous system (CNS) of unknown etiology. It is the most common non-traumatic cause of neurologic disability in young adults and affects between 250,000 and 400,000 persons in the United States^{11;12}. The disease usually manifests in the third to fourth decade of life and affects woman two to three times more commonly than men. In about 85% of patients, the course of disease starts with a period of unpredictable relapses and remissions (called relapsing remitting MS, or RRMS). After some number of years the majority of those patients will enter a phase of the disease where they develop slowly progressive disability (called secondary progressive MS, or SPMS). In another 15% of patients the disease onset is not marked by relapses, but rather by an insidiously progressive accumulation of disability. This subtype is called primary progressive MS (PPMS). Most treatments are only effective in RRMS.

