The discrepancies of the different BDNF levels might be explained by the difference of assays used. BDNF assays are now commercially available (RayBiotech, Norcross GA, USA). With this assay the minimum detectable dose of BDNF is typically less than 0.3 ng/ml without cross reactivity to other cytokines (Reproducibility - Intra-Assay: CV<10%, Inter-Assay: CV<12%).

4. Study Procedures

Study Design:

Phase 2 trial.

This selection study will be performed as a randomized, parallel Group Trial to determine the amount of FES ergometry required to achieve maximal CSF BDNF levels in individuals with inflammatory myelopathy.

Subjects will be randomized into 4 groups (FES1: 1 session of FES ergometry per week, FES3:3 sessions of FES ergometry per week, FES5: 5 sessions of FES ergometry per week, and Passive: 3 sessions of passive cycling per week). Session duration is 60 minutes. After obtaining a detailed physical and spasticity testing, baseline serum and CSF BDNF levels will be measured. The subjects will then receive

FES ergometry or passive cycling according to their group assignment for 3 weeks. At that time the subjects will return for a physical exam, spasticity testing, and repeat serum and CSF BDNF level testing. The primary investigator will be blinded to the results. The Study Time Line is found in Figure 1.

[figure not shown]

Figure 1: Study Time Line

Study Treatments

All activities will be conducted at INI and are supervised by a licensed physical therapist. This includes all cycling activities; all study procedures, the screening and final visits. Urine (for rapid urine pregnancy testing) will be sent to the Johns Hopkins Medicine (JHM) Pathology lab.

Functional Electrical Stimulation Ergometry

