CSF will be processed as previously described⁷⁷. Briefly, CSF will be processed with immediate decellularization by centrifugation and freezing at -80°C. CSF analyses will be done on paired samples using cytokine arrays (purchased from RayBiotech) according to manufacturer instructions.

i) Blood Draw (BDNF, PT/INR)

This is a routine procedure with an experimental analysis. Approximately 5ml of venous blood will be drawn from the upper or lower extremities during each scheduled procedure for a maximum total of 20ml in a 3 week period. Blood samples will be processed as previously described⁷⁸. Blood serum analyses will be done on paired samples using cytokine arrays for BDNF (purchased from RayBiotech) according to manufacturer instructions.

j) Mood assessment (using daily SMS text based Likert scale subjective measurement)

This is a routine assessment that is generally not part of the standard clinical exam at our center. We will assess mood on a Likert scale from 1 (low) to 10 (high) using “Mood24/7” (<http://www.mood247.com>). The use of this kind of mood assessment has been validated extensively and shown to correlate with a vast array of psychiatric mood rating scales⁷⁹. Subjects will sign up with “Mood24/7” online via the HealthCentral mood tracking tool that is licensed from Johns Hopkins at the beginning of the study. The subjects will receive an automated daily message from “Mood24/7” requesting input in regards to their mood. The study team will only check on the data at the end of the collection period and not during the collection. [name] serves as the mental health consultant in this study. If a subject were to express depressive symptoms at the end of the study, we will refer the subject to [name]. HealthCentral secures the confidentiality and privacy of patient data using industry best practices including documented standards and procedures for protecting sensitive data, encryption of data within the Mood24/7 database and tool interface, locking down all servers and network infrastructure supporting Mood24/7, limiting access to patient data to only employees that have a need, and special training for employees covering their responsibilities as far as protecting the confidentiality of sensitive data.

Study Duration and number of study visits required of research participants:

The study will last up to 4 weeks. The Study Time Line is found in Figure 1, and the Data Collection Schedule in Table 1.

Date: May 10, 2016

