Most individuals with inflammatory myelopathy have lost normal voluntary control of lower extremity function. Functional Electrical Stimulation cycling with the RT-300 allows the equivalent of 6000 step cycles in one hour (when cycling at 50 rpm), a little over half the normal number of steps a healthy adult takes on average per day. Six lower extremity muscle groups are simultaneously stimulated with this device. It is therefore the most efficient device in delivering electrical stimulation to subjects with complete spinal cord injury and was therefore chosen for this study.

The RT-300 FES bike has been FDA-cleared for use in general rehabilitation (the device clearance number is K072398). It has been a standard rehabilitation treatment modality at our center for several years.

7. Study Statistics

- a. Primary outcome variable.

BDNF CSF level testing

BDNF levels in the CSF of the study subjects will be measured in response to FES ergometry. BDNF has been linked to improved functional outcomes following CNS injury. We therefore chose BDNF as a surrogate marker to determine FES efficacy.

- b. Secondary outcome variables.

CSF analysis

Exploratory analysis to further understand the CSF response to FES cycle ergometry. It will be aimed at examining neurotrophins and define the molecular signature of repair in the CSF of patients with spinal cord injury.

Spasticity level:

Date: May 10, 2016
Principal Investigator: [name].
Application Number: NA_00041441

FES cycle ergometer therapy is expected to improve spasticity. This will be assessed by Modified Ashworth testing.

- c. Statistical plan including sample size justification and interim data analysis.

Sample size and power:

This is a dose finding clinical trial. Because there is limited data on BDNF CSF levels, the sample size cannot be computed at this time (power analysis cannot be performed). Instead we will use an adaptive sample size re-estimation strategy. Based on *in vivo* BDNF animal data we decided an effect size of 20% to be significant⁸⁰.

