After enrolling 48 subjects (12 per group) we will estimate 2 quantities: the mean BDNF CSF level per group and the within group standard deviation of BDNF levels (averaged across the 4 groups). The sample size may then be adjusted based on the estimated effect size (estimated mean per treatment group - 80% of that estimated mean) and the estimated standard deviation. If the recalculated total sample size is equal or less than 100 then the study will proceed. Otherwise the study will be terminated at that point.

The required sample size will be computed such that it provides 80% probability of correctly selecting the amount of FES that yields the highest mean BDNF given a true 20% mean difference between the highest mean and the next highest mean.

Analysis plan:

Dependent Variables: CSF BDNF concentration, Serum BDNF concentration, CSF GDNF concentration, CSF NT-3 concentration, CSF NT-4 concentration, CSF CNTF concentration, CSF NGF concentration, CSF IL-6 concentration, CSF IL17 concentration, CSF TNF α concentration, CSF IL-1 β concentration, CSF IL-23 concentration, CSF IL-12 concentration, modified Ashworth score, mood.

Independent Variables: Intervention (FES ergometry); Timing

Approach: The distributions of all outcome variables (CSF BDNF concentration, Serum BDNF concentration, CSF GDNF concentration, CSF NT-3 concentration, CSF NT-4 concentration, CSF CNTF concentration, CSF NGF concentration, CSF IL-6 concentration, CSF IL17 concentration, CSF TNF α concentration, CSF IL-1 β concentration, CSF IL-23 concentration, CSF IL-12 concentration, modified Ashworth score, mood) will be described by treatment group (mean, median, standard deviation). The group that has the highest mean change in BDNF concentration will be used for further studies (future Phase 3 clinical trial).

Exploratory analysis will be performed to compare mean values of GDNF, NT-3, NT-4, CNTF, NGF, IL-6, IL17, TNF α , IL-1 β , IL-23, IL-12 concentration among the 4 groups using analysis of variance or suitable non-parametric methods (Kruskal-Wallis Test) if the outcome appears to be non-normally distributed.

- d. Early stopping rules.

The principal investigator may discontinue the study if the interim statistical analysis as described above indicates that the number of subjects required for this trial exceeds #80.

Patients may withdraw from the study at any time for any reason. Any investigator may discontinue a patient for any of the following reasons:

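### The secondary objective concerns change in CSF cytokines, but the only test named in 7.c is a one-way comparison of group means that does not say how the Baseline sample enters

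*Combined protocol and SAP*

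**What the plan says.** Section 2 gives the secondary objective as "To quantify changes in the CNS inflammatory environment in response to FES ergometry in subjects with inflammatory myelopathy". Its hypothesis is that IL-6, IL17, TNF-alpha, IL-1beta, IL-23 and IL-12 "change in response to FES ergometry".

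The data for this are collected. The schedule in Section 4 has a lumbar puncture at Baseline and another at the Final (Week 3) visit, and item h of the assessments states that "CSF analyses will be done on paired samples using cytokine arrays".

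The Analysis plan in 7.c contains four relevant statements:

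- It lists "Independent Variables: Intervention (FES ergometry); Timing".
- All outcomes are to be described by treatment group (mean, median, standard deviation).
- The arm taken forward is the one with the largest average change in BDNF.
- For the other CSF markers, "Exploratory analysis will be performed to compare mean values of GDNF, NT-3, NT-4, CNTF, NGF" and the six cytokines "among the 4 groups using analysis of variance or suitable non-parametric methods (Kruskal-Wallis Test" being the alternative when the data look non-normal.

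Spasticity is a secondary outcome in 7.b: "This will be assessed by Modified Ashworth testing". It is rated at Baseline and Week 3. In 7.c it is among the outcomes described by group, but not among those compared.

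**The concern.** The objective and the analysis do not match. The hypothesis is about change over three weeks of cycling, whereas the named test compares group means of a value that is not identified. An analyst could use Week 3 concentrations, change scores or baseline-adjusted values for each of the 11 markers (five neurotrophins, six cytokines) and comply with 7.c each time. That choice could then be made with the data in view.

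Two things are at stake. If Week 3 values are compared, the precision available from a Baseline sample already taken by lumbar puncture is lost. And whichever value is chosen, a one-way test among arms gives no estimate of how much each arm changed, which is what the objective asks to be quantified.

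**Working it through.** **No figure to reproduce.** The plan gives no standard deviation, correlation, significance level or power for these markers. Its 80% target is a probability of correct selection and applies to BDNF only. What follows is therefore illustrative.

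**Inputs**

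- From 7.c: four groups, with 12 per group at the interim look (4 × 12 = 48).
- Assumed: SD = 1 at both visits, two-sided 5% level, 80% power for a pairwise difference, and a Baseline to Week 3 correlation r that is the same in all arms.

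**Step 1: residual variance by choice of value**

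- Week 3 value alone: 1
- Change score: 2(1 − r)
- ANCOVA (Week 3 adjusted for Baseline): 1 − r²

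**Step 2: detectable pairwise difference.** For the Week 3 value alone it is √(2/12) × (1.960 + 0.842) = 0.408 × 2.802 = 1.14 SD. ANCOVA multiplies this by √(1 − r²).

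| r (assumed) | 1 − r² | √(1 − r²) | Reduction | Detectable difference, ANCOVA |
|---|---|---|---|---|
| 0 | 1.00 | 1.000 | 0% | 1.14 SD |
| 0.3 | 0.91 | 0.954 | about 5% | 1.09 SD |
| 0.5 | 0.75 | 0.866 | 13% | 0.99 SD |
| 0.7 | 0.51 | 0.714 | 29% | 0.82 SD |
| 0.8 | 0.36 | 0.600 | 40% | 0.69 SD |

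The percentage reductions do not depend on the number per arm.

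**Step 3: power for a 1-SD pairwise difference, 12 per arm (normal approximation)**

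| r (assumed) | Week 3 alone | Change score | ANCOVA |
|---|---|---|---|
| 0 | 0.69 | 0.41 | 0.69 |
| 0.3 | 0.69 | 0.54 | 0.73 |
| 0.5 | 0.69 | 0.69 | 0.81 |
| 0.7 | 0.69 | 0.89 | 0.93 |

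The change score beats the Week 3 value only when 2(1 − r) < 1, that is, when r > 0.5. In this approximation ANCOVA is never worse than either. So ANCOVA is the better choice for comparing groups, and simply switching the test to change scores is not.

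**Step 4: what a between-group test cannot show.** Suppose all four arms shift by the same 0.5 SD. A four-group ANOVA of Week 3 values rejects at its nominal rate (0.048 in 10,000 simulated trials). ANOVA of change, or ANCOVA, would also miss such a shift, because the arms do not differ. A paired test pooled over 48 participants would detect it with power 0.67 at r = 0, 0.82 at r = 0.3, 0.92 at r = 0.5 and 0.99 at r = 0.7. Quantifying change therefore needs a separate within-arm estimate.

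**The case against.** The strongest reply is that 7.c is brief but does not ignore Baseline. It lists Timing as an independent variable for all outcomes, the CSF assays are run on paired samples, and Section 4 says "baseline serum and CSF BDNF levels will be measured" before cycling starts. The CSF marker work is called exploratory in both 7.b and 7.c, it is unpowered, and the only selection rule uses BDNF. Item (a) under the secondary objective speaks only of measuring concentrations, so the endpoint variable is left open; it is not fixed as change and then contradicted.

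Much of this stands, and it rules out several readings that a reader might infer:

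- **That the Baseline lumbar puncture goes unused.** The documents do not support this. The Baseline sample is needed for the BDNF change that selects the arm. For the other markers the text is silent and does not exclude Baseline. Listing Timing does not fill the gap, however, because the one-way tests named have no place for it.
- **That chance imbalance at Baseline would bias the comparison.** The trial is randomised, so Week 3 means are unbiased for differences between arms, and the ANOVA error term already reflects chance imbalance. The loss is one of precision.
- **That between-person spread in these cytokines is known to be wide because diagnoses are mixed.** No Baseline cytokine SDs are given for this population.
- **That a within-arm change would establish an FES effect.** It is an uncontrolled before-after estimate, open to time trends and regression to the mean.
- **That spasticity is ignored.** It is summarised by group. BDNF has no between-group test either, because this is a selection design.

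What remains is that 7.c leaves the analysed value open, names no estimate of change, and passes over a more precise comparison that needs no new data.

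**Conclusion.** The point holds in this limited form. The secondary hypothesis is about change, while the single inferential analysis named is a one-way comparison of unspecified means with no baseline covariate, change score or within-arm estimate.

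If Week 3 values are used, the detectable difference is larger than it need be. Baseline adjustment would cut it by about 5% to 40% for r between 0.3 and 0.8, and by nothing at r = 0. These figures rest on an assumed r, equal variances at the two visits and a common linear relation to Baseline. The documents supply none of these, and r may differ between markers. The missing estimate of change does not depend on r.

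The consequence is moderate. The analysis is exploratory and no decision rule depends on it, but Section 2 states a formal secondary hypothesis and the plan should say how it will be addressed.

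**What to change.** In 7.c, replace the one-way comparison with the following:

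1. For each neurotrophin and cytokine, compare the four groups by ANCOVA of the Week 3 value with the Baseline value as covariate, on the log scale or rank-based if the distribution is skewed.
2. Report the mean Baseline to Week 3 change in each arm with its confidence interval. Label it descriptive, because it is an uncontrolled before-after estimate, and read the FES effect from the contrasts with passive cycling.
3. Analyse Modified Ashworth in the same baseline-adjusted way, rank-based because the scale is ordinal.
4. State what Timing means and where it enters, and keep the whole set labelled exploratory.

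The cost is a change of wording and a slightly longer analysis. Both CSF samples and both Ashworth ratings are already scheduled, so no visit, sample or participant burden is added. Each ANCOVA spends one degree of freedom on the covariate, a small loss if r turns out to be near zero.

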Principal Investigator: [name].
Application Number: NA_00041441

Study Assessments:

The following post-consent screening will be performed at the Screening Visit (Week -1):

- a. Medical History (about 30 minutes)
- b. Physical Exam (about 30 minutes)
- c.
- d.
- e. Fast Urine Pregnancy Test (about 15 minutes)
- f.

The subject eligibility criteria will be reviewed after the Screening Visit.

The following assessments will be performed at the FES Trial Visits:

- a. FES trial (about 30 minutes)

The subject eligibility criteria will be reviewed after the FES Trial Visit. Participants who fail the FES trial will be excluded from the study. If the subject is willing and able to proceed with the study the subject will be signed up with "Mood24/7", and scheduled for the Baseline visit.

The following assessments will be performed at the Baseline (Week 0) visit:

- a. Vital Signs (about 5 minutes)
- b. Modified Ashworth Scale (about 15 minutes)
- c. Concomitant Medication (about 10 minutes)
- d. Lumbar Puncture (about 30 minutes)
- e. Blood Draw (about 5 minutes)

The following assessments will be performed at the Final (Week 3) visit:

- a. Physical Exam (about 30 minutes)
- b. Vital Signs (about 5 minutes)
- c. Modified Ashworth Scale (about 15 minutes)
- d. Concomitant Medication (about 10 minutes)
- e. Lumbar Puncture (about 30 minutes)
- f. Blood Draw (about 5 minutes)
- g. Mood assessment review (about 5 minutes)

	Screening	FES Trial	Baseline	Final
	1 ¾ hours	½ hours	1 ¾ hours	1 ¾ hours
Medical History	√			
Physical Exam	√			√
Vital Signs			√	√
Modified Ashworth			√	√
Fast Urine Pregnancy	√			
Concomitant Medications			√	√
FES Trial		√		
Lumbar Puncture			√	√
Blood Draw			√	√
Mood				√

Table 1: Data Collection Schedule

Study Treatment:

The total number of treatment visits depends on the study group:

- Group FES 1: a total of 3 FES ergometry visits scheduled 1 hour, 1 time a week for 3 weeks.
- Group FES 3: a total of 9 FES ergometry visits scheduled 1 hour, 3 times a week for 3 weeks.
- Group FES 5: a total of 15 FES ergometry visits scheduled 1 hour, 5 times a week for 3 weeks.
- Group Passive: a total of 9 passive ergometry visits scheduled 1 hour, 3 times a week for 3 weeks.

Blinding:

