Upon completion of the study, participants will be referred back to their treating SCI specialist who will be made aware of the treatment and follow-up. The same protocol will be followed for patients who terminate the study early. In the event of discontinuation due to adverse event, participants will be followed by the PI until resolution or stabilization of their adverse condition and then referred back to their treating SCI specialist.

5. Inclusion/Exclusion Criteria

Inclusion criteria

1. History of inflammatory myelopathy with onset at least 3 months prior.
2. Males and females between the ages of 18 and 65 years inclusive.
3. No FES ergometer (i.e. RT300 or equivalent) use within 4 weeks.
4. Ability to comply with procedures and follow-up.
5. Participants must be medically stable with no recent (1 month or less) inpatient admission for acute medical or surgical issues.
6. Access to a telephone with texting capabilities (SMS).
7. English language proficiency.

Exclusion criteria

1. Cardiovascular disease as defined by previous myocardial infarction, unstable angina, requirement for anti platelet agents, congestive heart failure, or stroke NYHA Class III or IV, history of arrhythmia with hemodynamic instability.
2. Uncontrolled hypertension (resting systolic BP>160mmHg or diastolic BP >100mmHg consistently).
3. History of epileptic seizures.

Date: May 10, 2016

Principal Investigator: [name].

Application Number: NA_00041441

4. Subjects who have a pacemaker, an implanted defibrillator or certain other implanted electronic or metallic devices other than baclofen pumps.
5. Subjects who are unwilling to agree to two CSF examinations (lumbar punctures).
6. Unstable long bone fractures of the lower extremities.
7. Pregnancy.
8. Subjects having Stage 2 or greater sacral decubitus ulcer.
9. Subjects with history of inability to tolerate electrical stimulation.
10. Malignancy.
11. Active drug or alcohol use or dependence that, in the opinion of the site investigator, would interfere with adherence to study requirements.

6. Drugs/ Substances/ Devices

- a. The rationale for choosing the drug and dose or for choosing the device to be used.
- b. Justification and safety information if FDA approved drugs will be administered for non-FDA approved indications or if doses or routes of administration or participant populations are changed.
- c. Justification and safety information if non-FDA approved drugs without an IND will be administered.

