The risks of a lumbar puncture are rare and include back pain, leg pain, headache, bleeding, infection, paralysis, brainstem herniation and death. About 10% of people develop a headache after a lumbar puncture. This headache may require prolonged bed rest and in some cases a blood patch in the area where the lumbar puncture was done. **To minimize the risk**, lumbar punctures will be done only in approved outpatient facilities by a certified neurologist with experience at performing this procedure.

Blood draw

Date: May 10, 2016
Principal Investigator: [name].
Application Number: NA_00041441

There risks of drawing blood include discomfort, bleeding or bruising where the needle enters the body, and in rare cases, fainting or infection. **To minimize the risks,** a trained nurse will draw the blood.

Other Risks:

Time Commitment

The time commitment for the treatment over the 3 weeks may be inconvenient. **To minimize the risks:** 1] The subject should contact the study coordinator if having problems scheduling the visits; 2] If we feel that the subject can not commit the time and effort, he/she will be excluded from the study; 3] The visits may cause moderate social, school and work disruption. The start of the study will be scheduled to lessen the disruption.

- c. Plan for reporting unanticipated problems or study deviations.

Data and Safety Monitoring Plan:

The data and safety monitoring plan has two components: internal monitoring by the PI, and periodic monitoring by the Johns Hopkins Medical Institutional Review Board.

Internal monitoring: This will be conducted under the supervision of the PI. The PI will work very closely with the study team evaluating every step of the study milestones. The PI will also oversee the review of the patient history as also the thoroughness of the completed case report forms in conjunction with all study measures. The PI will also supervise the quality of the data entry and data quality. This will ensure continuous close monitoring for safety assessments and study measurement outcomes. The PI will report unanticipated problems or study deviations in writing to the KKI Office of Research Administration and JHM-IRB.

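### The second lumbar puncture falls at the last scheduled visit, and the readable text schedules no adverse-event check after it, so its complications would reach the study only by passive routes

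*Combined protocol and SAP*

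**What the plan says.** **Schedule.** Lumbar punctures are listed at Baseline (Week 0) and at Week 3. Section 4 introduces the second set of procedures with "The following assessments will be performed at the Final (Week 3) visit". After the puncture that list has only a blood draw and a mood review. Final is the last column of Table 1. Neither the visit lists nor Table 1 has an adverse-event item, and adverse events are not among the outcome variables in section 7.

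**Follow-up.** The end-of-study text in section 4 refers completers back to their treating SCI specialist. It then says: "In the event of discontinuation due to adverse event, participants will be followed by the PI until resolution or stabilization of their adverse condition". No equivalent sentence covers a subject who completes the study.

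**Risk.** The lumbar puncture paragraph in section 8 opens with "The risks of a lumbar puncture are rare and include back pain, leg pain, headache, bleeding, infection, paralysis, brainstem herniation and death". It continues: "About 10% of people develop a headache after a lumbar puncture. This headache may require prolonged bed rest and in some cases a blood patch". The mitigation given concerns the facility and the operator's experience.

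**Monitoring.** Section 8c says that PI supervision will give continuous, close safety monitoring. It also provides for written reports of unanticipated problems, notice to the IRB and a pause in enrollment after any serious adverse event, and medical questions to the PI.

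**The concern.** The complications that section 8 lists follow the procedure, and for the second puncture the scheduled contact ends with the procedure visit. A subject who completes the study and then develops a headache, an infection or bleeding has not discontinued, so the one sentence promising PI follow-up does not apply.

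Two things are at stake. First, the pause in enrollment after a serious adverse event works only if the event becomes known, and no contact is scheduled at which a late event from the final puncture would be asked about. Second, any lumbar puncture complication rate that the trial reports would depend on spontaneous reports for up to half of the punctures, and so would probably be too low.

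The risk paragraph also disagrees with itself: headache is in a list described as rare, and is then given a frequency of about one in ten.

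**Working it through.** **1. Is any study time left after the final puncture?**
- Inputs: screening at Week -1 and the Final visit at Week 3 (section 4, Study Assessments); study length of at most 4 weeks (section 4, Study Duration).
- 3 - (-1) = 4 weeks. This reproduces the stated length and leaves 0 weeks after the Final visit.
- Final visit items in listed order: 30 + 5 + 15 + 10 + 30 + 5 + 5 = 100 minutes, against 1 3/4 hours (105 minutes) in Table 1.
- After the puncture: 5 + 5 = 10 minutes of listed items, or at most 105 - 90 = 15 minutes of the slot.

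**2. What share of punctures is affected?**
- With two punctures per subject and no dropout, the share is 1/2.
- With a fraction d lost before Week 3, it is (1 - d)/(2 - d). For assumed d of 10%, 20% and 30%, this is 47%, 44% and 41%.

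**3. How many headaches?**
- Inputs: about 10% (section 8), applied to each final puncture; 4 x 12 = 48 subjects at the interim look (section 7c). The final size is not fixed: section 7c uses a limit of 100 and section 7d a limit of 80, so both are shown.
- Expected number after the final puncture = N x rate, with all subjects completing:

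| N | 5% (assumed) | 10% (protocol) | 15% (assumed) |
|---|---|---|---|
| 48 | 2.4 | 4.8 | 7.2 |
| 80 | 4.0 | 8.0 | 12.0 |
| 100 | 5.0 | 10.0 | 15.0 |

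- Chance of at least one in 48 at 10%, with subjects independent: 1 - 0.9^48 = 0.994.
- With an assumed 20% dropout in 48: 4.8 x 0.8 = 3.84 expected.

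**4. Which stated provisions reach a completer after Week 3?**
- PI follow-up to resolution (section 4): no, because it requires discontinuation for an adverse event.
- Return to the treating specialist (section 4): yes, but no report back to the study is described.
- Medical questions to the PI, and hospital services after an injury (section 8c): yes, if the subject makes contact.
- IRB notice of serious events and PI reports of unanticipated problems (section 8c): yes, once the event is known.
- Daily text message (section 4, item j): it asks only about mood, and the team reads the data only when collection ends.

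None of these is a scheduled enquiry about adverse events.

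**The case against.** The best defence is that the protocol is not silent. The treating specialist is told about the treatment, the subject can contact the PI, hospital services are available, and the duty to notify the IRB of serious events is not limited to scheduled visits. Case report forms are mentioned and could include an adverse-event page. This stands in part: it rules out saying that complications could not become known. It does not supply an active check or a time window.

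Several stronger readings are tempting, and the documents do not support them:

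- **The gap applies equally to both punctures.** After the baseline puncture, subjects are due to attend 3 to 15 supervised sessions, then a physical exam and a medication review. A headache could well come to light there, although no item asks for it.
- **Subjects with a complication have nobody responsible for them.** The referral and the routes to the PI contradict this.
- **Headache is the most frequent risk.** It is the only risk given a number. Pain at the stimulation site and blood-draw discomfort have no stated rate, so no ranking is possible.
- **Each subject faces a 19% risk over two punctures.** That is 1 - 0.9^2 and needs independence within a person. The figure is 10% if susceptibility is fully shared and 20% if the two events never coincide. The text says only that about 10% of people are affected.
- **The complication rate decides whether later studies can use blood.** Section 9 makes that depend on whether plasma and CSF BDNF correlate.
- **Every expected headache starts after the visit ends.** The documents give no onset time. The counts are for headaches after the final puncture, with only 10 to 15 minutes of that visit remaining.

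**Conclusion.** The point holds in a limited form. In the readable text, no scheduled adverse-event check follows the final lumbar puncture, and the stated PI follow-up does not cover completers. Complications of that puncture would reach the study only by passive routes, which is less than section 8c claims.

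At the protocol's own rate the situation is almost certain to arise: about 4.8 headaches in 48 completers, with a range of 2.4 to 7.2 for assumed rates of 5% to 15%. This rests on reading the 10% as a rate per puncture and on no dropout; dropout lowers the count in proportion.

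The conflict between rare and about 10% is a separate inconsistency of wording in the same paragraph.

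Nothing here affects the choice of the group with the highest mean BDNF change. The conclusion also depends on two items that could not be read: Figure 1 and the consent pages, either of which might describe a later contact.

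**What to change.** 1. Check Figure 1 and the consent pages. If a contact after the final puncture is already described, bring it into the visit lists and Table 1.
2. Add an adverse-event row to Table 1, covering the cycling sessions and the Final visit.
3. Add one scheduled telephone or text safety contact after each puncture, including the final one. The investigators should set the window.
4. Reconcile the follow-up sentence in section 4 with the monitoring statement in section 8c, so that the position of a completer with an open or later-starting event is clear.
5. Reconcile the two statements on headache in the lumbar puncture paragraph of section 8. If a figure over two punctures is wanted, its dependence assumption should be stated.

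The cost is a small amendment and one or two short contacts per subject by existing staff. A telephone with texting is already an inclusion criterion. Participation ends slightly later, and the recorded complication rate will probably be higher than under spontaneous reporting.
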